Statistical Analysis Plan

Study Title: Brain Biomarkers of Response to Treatment for Apraxia of Speech

NCT#: 02046941

Date: 1-9-2014

Data Analysis

Behavioral Data. Treatment effect sizes for treated and untreated items were calculated separately for each sound target using the Busk and Serlin (1992) d_2 statistic. This effect size is derived by calculating the difference between the average performance from the comparison design phases (e.g., M_{A1} and M_{A2}) and dividing this difference by the pooled standard deviation of the two phases:

$$d_2 = \frac{M_{A2} - M_{A1}}{SD_{pooled}}$$

where M_{A1} was based on the final five probe trials during the baseline phase prior to treatment, and M_{A2} was based on the final three probe trials at the end of the treatment phase (consistent with prior SPT studies; Wambaugh et al. 2013). For participants who were trained on more than one target sound, the d_2 value represents the average d_2 across targets (Beeson & Robey, 2006). Based on previous SPT research (Bailey et al., 2015), the cut-off value for what was considered a large effect size for treated items was $d = 9.6$, $d = 7.0$ for a medium effect size, and $d = 5.2$ for a small effect size. The cut-off values for untreated items were $d = 6.7$ for large effect size, $d = 3.8$ for medium effect size, and $d = 2.2$ for small effect size.

MRI Data. To relate treatment effect size to lesion site, participants' normalized lesions were first visualized in MRIcron and overlaid on the automated anatomical labeling (AAL) atlas, which is based on 116 parcellations of the brain (Tzourio-Mazoyer et al., 2002). We focused on 4 regions of interest (ROIs) that have been previously implicated in AOS, SPGI, Broca's area, SMG, and pre-central gyrus. The percentage of each AAL region affected by an individual's lesion was then calculated in MRIcron. Participants' behavioral data (effect size) and individual anatomical lesion data were analyzed using a Partial Least Square (PLS) regression: Effect size was related to the lesion variables in a leave-one-out manner.

For the white matter analysis, T1 anatomical images were processed using FreeSurfer 5.3, which includes intensity normalization, segmentation, inflation of surfaces to spheres, and spherical registration of spherical surfaces to a standard template (Dale et al., 1999; Fischl et al., 1999). FreeSurfer provides neuroanatomical parcellation of the cortex, defined by Desikan-Killiany (Desikan et al., 2006). It was necessary to virtually implant 20mm of the medial-most portion of the right hemisphere onto the

left hemisphere in order to fill in holes created by the large lesions in the left hemisphere that prevented the Free Surfer program from completing processing. This virtual implant into the left hemisphere using FreeSurfer has negligible effects on cortical thickness measurements and Desikan parcellations in the right hemisphere (Solodkin et al, 2010). FreeSurfer also provides labels of the segmented subcortical structures, some of which are termination zones of white matter structures investigated in the current study (Abe et al., 2010; Fischl et al., 2002; Fischl et al., 2004).

We wanted to limit the number of possible comparisons for analysis. Therefore, the analyses were confined to a subset of Desikan-Killiany regions previously implicated in imaging studies of speech and language treatment: Broca's area homologue in ventrolateral prefrontal cortex, precentral cortex, insular cortex, inferior parietal cortex, superior temporal sulcus, and middle and superior temporal cortices. Thickness measurements were computed by FreeSurfer and then averaged over the chosen Desikan parcels. Thickness measurements have been shown to be stable across scanning sessions (Han et al 2006), and particularly reliable in Desikan parcels within an individual (Wang et al 2010).

The mean images from realigned B_0 and diffusion-weighted images (DWIs) were coregistered to individuals' anatomical images after distortions were corrected using field maps (Jezzard & Balaban, 1995; Jones & Cercignani, 2010). The mean images from realigned B_0 and DWIs were co-registered and resampled to a high-resolution anatomical image space using the entropy-based algorithm in SPM8 (www.fil.ion.ucl.ac.uk/spm/). Mean images were used to increase the stability of the coregistration (Rohlfing et al., 2005). The individual B_0 and DWIs were then re-aligned and resampled to their respective mean images. FA was computed using the standard formula from the eigenvalues of the tensor (Basser & Pierpaoli, 1996; Pajevic & Basser, 2003) and was averaged in selected fiber tracts.

Average FA was calculated for white matter tracts in the right hemisphere based on probabilistic atlases (Mori et al., 2008; Oishi et al., 2008). The skull-stripped brain volume from each participant's T1 image was normalized to MNI305 template space (Evans et al., 1993) using FreeSurfer, and each normalized brain image was then coregistered to the ICBM template containing the probabilistic tract atlases (Mazziotta et al., 2001). Then the FA data, coregistered to the T1 image, were sampled in ICBM space using a tract threshold of 25% probability and then averaged. The analyses focused on four white matter tracts previously implicated in speech-language recovery/treatment: the inferior longitudinal fasciculus

(ILF), the inferior frontal occipital fasciculus (IFOF), the superior longitudinal fasciculus (SLF, fronto-temporal component), and the uncinate fasciculus (UF).

The percent change in FA values and cortical thickness from pre- to post-SPT was calculated as:

$$Diff(A, B) = \frac{A - B}{(A + B)/2} \times 100\%$$

where A is the post-MRI value and B is the pre-MRI value. We report both descriptive statistics and correlation coefficients relating treatment effect size to FA and cortical thickness changes.

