## **Study Protocol**

### **Behavioral Protocol**

Performance on the pre-testing measures was used to identify candidate target sounds for the SPT protocol for each individual. Up to 3 target sounds were identified for each participant, as in previous studies with SPT (see Bailey et al., 2015). The targets sounds were single consonants or clusters tested at the word level (see Table 1). Lists of 16-20 words with the target sounds were generated and administered to participants during subsequent pre-treatment sessions. For every target sound, two lists of 8-10 words each were generated in order to have a trained and untrained item list. The trained list(s) were those items that were trained/treated using SPT during the treatment phase. For the probe trials, participants were asked to simply repeat each word in the list spoken by the SLP. At least 5 baseline probe trials were conducted prior to treatment, and performance had to fall between 50-100% errors for each target to be included in the treatment phase. This criterion ensured a sufficiently low baseline to minimize ceiling effects in the behavioral data during treatment. Also, performance on the final three probe trials prior to treatment had to fall within 15% of each other, in order to establish a stable baseline; otherwise, the baseline phase was extended until this criterion was met (see Fisher et al., 2003).

Following the pre-treatment (baseline) phase, the treatment phase consisted of the SPT protocol delivered to participants in 1-hour sessions, 3 days a week, for a total of 16 sessions over 5.5 weeks. The SPT protocol was the same as that developed and extensively studied by Wambaugh and colleagues (see Wambaugh & Nessler, 2004). Table 2 shows the SPT hierarchy, which involves verbal repetition, imitation, and articulatory placement cueing. The same list(s) of 8-10 trained items developed during the baseline phase were trained using this hierarchy throughout the 5.5 week period.

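### d2 can depend on baseline accuracy, yet no brain-behaviour analysis shows a baseline-adjusted result beside the raw one

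*SAP*

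**What the plan says.** The Protocol (Behavioral Protocol) sets the entry rule: "performance had to fall between 50-100% errors for each target to be included in the treatment phase". It gives the purpose: "This criterion ensured a sufficiently low baseline to minimize ceiling effects in the behavioral data during treatment". A stability rule adds that "performance on the final three probe trials prior to treatment had to fall within 15% of each other". Probe lists are short: "two lists of 8-10 words each were generated" for each target sound, one trained and one untrained.

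The SAP (Data Analysis, Behavioral Data) divides the change in mean percent correct by the pooled SD of the two phases. It fixes the baseline mean as follows: "M_{A1} was based on the final five probe trials during the baseline phase prior to treatment". The end-of-treatment mean rests on fewer probes: "M_{A2} was based on the final three probe trials at the end of the treatment phase". With several targets, a participant's d2 is the mean over targets.

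For lesion site, the SAP (Data Analysis, MRI Data) plans a PLS regression: "Effect size was related to the lesion variables in a leave-one-out manner". For FA and cortical thickness it states: "We report both descriptive statistics and correlation coefficients relating treatment effect size to FA and cortical thickness changes". Neither analysis names baseline accuracy, severity or any other covariate.

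**The concern.** Baseline accuracy enters d2 in two ways. First, it limits the numerator: a target at 0% can gain 100 points, a target at 50% only 50. Second, it affects the denominator: with a short word list, probe-to-probe variation is small near 0% correct and largest near 50%. Both push d2 down as baseline accuracy rises, for a given final performance. Subtracting baseline in the numerator does not in general remove this dependence.

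If a brain measure is itself related to starting accuracy, a raw association with d2 may partly restate where participants began. The study seeks brain biomarkers of treatment response, so a reader would want to know whether an association goes beyond starting accuracy. The planned output does not show that.

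**Working it through.** The plan states no sample size, test or significance level, so there is no figure of its own to reproduce.

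**Inputs from the documents.** Baseline 0-50% correct; 8-10 words per list; 5 baseline and 3 end probes; treated-item cut-offs of 5.2 (small), 7.0 (medium) and 9.6 (large).

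**Assumptions.** Binomial probes; pooling weighted by degrees of freedom (4 and 2), since the SAP does not give the weights; a two-sided 5% test as a yardstick; sample size and brain-baseline correlation as stated below.

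**Step 1: d2 at the same final accuracy.** With baseline p0, end accuracy p1 and k words:

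SD_pooled = 100 × sqrt{[4·p0(1−p0) + 2·p1(1−p1)] / (6k)}, and d2 ≈ 100(p1 − p0) / SD_pooled.

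For k=10, p0=0.05, p1=0.80: SD = 100 × sqrt[(4×0.0475 + 2×0.16)/60] = 100 × sqrt(0.0085) = 9.2, so d2 = 75/9.2 ≈ 8.1.

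| Baseline | Gain to 80% | Pooled SD, 10 words | d2, 10 words | d2, 8 words |
|---|---|---|---|---|
| 5% | 75 | 9.2 | 8.1 | 7.3 |
| 20% | 60 | 12.6 | 4.7 | 4.2 |
| 40% | 40 | 14.6 | 2.7 | 2.4 |
| 50% | 30 | 14.8 | 2.0 | 1.8 |

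The same final performance runs from above the medium cut-off to below the small one.

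**Step 2: the denominator alone.** With the gain fixed at 40 points and 10 words, d2 is 4.5, 3.7, 2.9 and 2.9 at baselines of 0, 5, 20 and 50%. The denominator effect lies mainly below about 20% correct. Above that, the numerator drives the result.

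**Step 3: the stability rule.** With everyone ending at 90% and 10 words, the formula gives 10.8, 6.0 and 2.9 at baselines of 5, 20 and 50%. Simulated probes that obey the 15% rule (read as 15 percentage points) and the 50% entry limit give median d2 of 11.7, 7.0 and 3.9. The ratio of highest to lowest falls from 10.8/2.9 = 3.7 to 11.7/3.9 = 3.0. The two sets are not strictly comparable, because one is a median of simulated d2 and the other a plug-in ratio. The rule appears to narrow the spread without removing it.

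**Step 4: consequence for a brain-d2 correlation.** Simulated rejection rates at 5%, with a brain measure that correlates 0.5 with baseline and has no further link to outcome:

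| Response model | Raw | Adjusted for baseline |
|---|---|---|
| Final accuracy unrelated to baseline | 16% (n=12), 25-27% (n=20), 29-34% (n=24) | about 5% |
| Constant gain in points (40, SD 10) | 5.4% (n=12), 6.5% (n=20) | 4.4%, 5.0% |
| Constant gain in logits | 5.6% (n=12), 5.9% (n=20) | about 5-6% |

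The ranges in the first row come from runs without and with the stability rule. That row is sensitive to its settings. Another run with two targets and 10 words gave 20%, 33% and 40% at n=12, 20 and 24, against 4-5% adjusted. With final accuracy about 85% (SD 7 points), two targets and the stability rule, the raw rate was 16%, 35% and 46% at n=10, 20 and 30, against 3-6% adjusted. In those last settings d2 correlated about −0.73 to −0.78 with baseline accuracy. With a brain-baseline correlation of 0, raw and adjusted rates both stayed at about 3-6%. That last set used 300 replicates per cell, so its Monte Carlo standard error is at most sqrt(0.25/300) = 2.9 points.

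**The case against.** The strongest reply is that d2 is defined as change, and change is what the trial calls response. If everyone reaches the same final distribution, a participant who started lower did gain more. A brain measure tied to baseline is then truly related to gain: in one simulation of this case its mean correlation with true gain was about −0.39. Calling that a false positive swaps change for final accuracy given baseline, which is a choice of estimand. This stands. So does its companion: where gain is unrelated to the brain measure, in points or logits, the raw rate is close to 5%, so the denominator artefact alone adds little.

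Three further points stand.
- The link between brain measure and baseline is assumed. It is most plausible for lesion load in regions chosen for their association with apraxia of speech. It is weaker for pre-to-post change in the right hemisphere, where stable differences between people are largely removed.
- M_A1 is accuracy on up to three selected sounds, restricted to 0-50% correct. It is a proxy for severity; a mildly affected participant may have one sound near the floor.
- The SAP promises coefficients and names no test, so the rejection rates are a yardstick and not a stated property of the plan.

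The entry rule is a real safeguard, but its stated aim is to minimise ceiling effects. It still leaves a two-fold range in attainable gain.

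**Conclusion.** The concern holds in a limited form. By construction d2 can depend on baseline accuracy, and neither the lesion PLS nor the FA and thickness correlations carries a baseline term. An association with d2 may therefore partly reflect starting accuracy on the selected targets. With an assumed brain-baseline correlation of 0.5, the effect on the raw rejection rate ranges from almost none to roughly 16-34% for n of 12 to 24, and higher in some settings. Which applies turns on the response model, about which the documents say nothing.

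A reader might infer that the planned correlations are invalid, or that a severity effect will be mistaken for a biomarker at those rates. The documents do not support that. They give no brain-baseline correlation and no sample size, and nothing in them favours the one response model that produces the inflation. Nor do they show that only a baseline-adjusted association can count as evidence of response.

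What remains is a cheap improvement: adjustment kept the rate near 5% under all three response models, and it would show whether an association goes beyond starting accuracy.

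**What to change.** Keep every raw result and place an adjusted one beside it, using M_A1 averaged over a participant's targets:

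- **FA and thickness change:** partial correlation with d2 given mean M_A1.
- **Lesion PLS:** within each training fold, regress both d2 and the lesion variables on mean M_A1, fit the PLS to the residuals, and apply the same fold's coefficients to the participant left out.
- **Diagnostic:** report the correlation of d2 with mean M_A1, so the reader sees how strong the dependence is in these data.
- **Wording:** describe a brain measure as related to response independent of starting accuracy only if the adjusted association agrees with the raw one.

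The cost is SAP wording and a few lines of code, since M_A1 is already computed for every d2. Adjustment uses one degree of freedom, which matters if the sample is small. It also gives a conservative estimate if a brain measure acts on response through severity, which is a reason to show both results.
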